In May 2019, the EC requested a reassessment of the benefit-risk of tofacitinib pursuant to Article 20 of Regulation (EC) No 726/2004 due to a signal for increased risks of pulmonary embolism and mortality arising in an ongoing Pfizer-sponsored Phase 3b/4 safety study (A3921133) designed to evaluate the risk of malignancy and major adverse cardiac events in RA patients aged 50 years and older who had at least one cardiovascular (CV) risk factor. In November 2019, the Committee on Human Medicinal Products (CHMP) concluded, based on a recommendation from the Pharmacovigilance Risk Assessment Committee (PRAC), that patients treated with tofacitinib are at increased risk of venous thromboembolism (VTE) events, both for deep venous thrombosis as well as pulmonary embolism, especially in patients with risk factors for VTE. The PRAC further concluded that the risk of VTE events is dose-dependent. To minimise this risk, the PRAC recommended that warnings be added to the Summary of Product Characteristics (SmPC) regarding the increased risk of VTE observed in patients taking tofacitinib, especially for patients with known risk factors for VTE. The PRAC also recommended that treatment with tofacitinib be discontinued in patients with suspected VTE and that tofacitinib 10 mg BID for maintenance treatment is not recommended in patients with UC who have known VTE risk factors unless there is no suitable alternative treatment available. Clarifications on the posology were also added, particularly for UC patients in maintenance. Specifically, some patients (i.e., patients who failed to respond to alternative treatment options for UC such as tumour necrosis factor [TNF] inhibitor treatment) who had a reduction in response to 5 mg BID maintenance treatment may benefit from an increase in maintenance dose to 10 mg BID; for these patients, the presence of known risk factors for VTE should be considered. However, tofacitinib 10 mg BID for maintenance treatment should be used for the shortest duration possible.

The PRAC also concluded that, based on the interim analyses of Study A3921133, there is a potential increased risk of mortality. This was partly driven by an increased risk of serious infections among patients 65 years and older. As such, tofacitinib should be considered

among patients 65 years and older only if no suitable alternative treatment is available. These conclusions and revisions to the SmPC were approved by the EC on 31 January 2020.

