As a result of the Article 20 benefit-risk reassessment, the MAH will additionally evaluate HCPs' compliance with the new PRAC recommendations and limitations for use to minimise the risk of VTE across all approved indications (i.e., tofacitinib should be used with caution in patients with known VTE risk factors regardless of indication and dosage), with additional focus on the use of tofacitinib 10 mg BID as a maintenance treatment for patients with UC, and use and prior treatments among patients aged 65 years and older treated with tofacitinib. The MAH will also examine tofacitinib prescribing patterns over time, as well as changes in the utilisation of tofacitinib among patients with VTE risk factors and among elderly patients aged  $\geq 65$  years following the updated recommendations and limitations for use. As a result of the 2021 signal evaluation procedure, the MAH will also assess HCPs' compliance with the new EMA recommendations and limitations for use related to tofacitinib use in patients with CV risk factors and use in patients with malignancy risk factors.b The MAH will also examine tofacitinib prescribing patterns over time in the 2021 signal evaluation procedure.

This protocol describes the drug utilisation study (i.e., component 2 described above). Data from this study, together with the findings from the tofacitinib prescriber survey (A3921334), will be used to assess whether the aRMM materials are effective. This non-interventional (NI) study is designated as a Post-Authorisation Safety Study (PASS) and is conducted by the MAH as a Category 3 commitment to the EMA.

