History of malignancy (non-metastatic and metastatic; excluding non- melanoma skin cancer)	Outcome: VTE risk factor	Defined as ≥1 ICD-10 diagnosis code for malignancy (excluding non-melanoma skin cancer) in the 12 months prior to or on the day of the index tofacitinib dispensing.
Age >50 years at tofacitinib initiation	Outcome: VTE risk factor	Defined as age at tofacitinib initiation >50 years.
History of diabetes	Outcome: VTE risk factor	Defined as $\geq 1$ ICD-10 diagnosis code for diabetes in the 12 months prior to or on the day of the index tofacitinib dispensing.
History of hypertension	Outcome: VTE risk factor	Defined as ≥1 ICD-10 diagnosis code for hypertension in the 12 months prior to or on the day of the index tofacitinib dispensing.
Initiating tofacitinib with ≥1 VTE risk factor	Outcome: VTE risk factor	Defined as ≥1 VTE risk factor (as listed and defined above) identified in the 12 months prior to or on the day of the index tofacitinib dispensing (unless otherwise specified).
Number of VTE risk factors identified prior to tofacitinib initiation	Outcome: VTE risk factor	Calculated as the sum of the number of VTE risk factors (as listed and defined above) identified in the 12 months prior to or on the day of the index tofacitinib dispensing (unless otherwise specified).

Table 3.	Operational	definitions of	f study	variables in	the selected	databases
----------	-------------	----------------	---------	--------------	--------------	-----------

Variable	Role	Operational definition
Number of UC patients with: ≥1 VTE risk factor; no prior alternative therapy (i.e., biologic); and an ADD >10 mg in Weeks 16-23, Weeks 24- 31, Weeks 32-39, and Weeks 40-47 of follow-up t	Outcome: VTE risk factor	Defined as a patient meeting all of the following criteria: ≥1 ICD-10 diagnosis code for UC; ≥1 VTE risk factor (as listed and defined above); 0 prescription medication dispensings for a biologic (as identified by ATC codes) in the 12 months prior to and including the date of the index tofacitinib prescription dispensing; and an ADD of >10 mg in Weeks 16-23, Weeks 24-31, Weeks 32- 39, and Weeks 40-47 of follow-up, respectively (ADD defined in Section 9.3.4). Complete list of biologics in ANNEX 6. LIST OF ATC CODES FOR MEDICATIONS OF INTEREST TO AVOID WHILE TAKING TOFACITINIB.

 Table 3.
 Operational definitions of study variables in the selected databases

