Assessment of VTE risk factors while receiving tofacitinib therapy (duration of tofacitinib therapy defined in Section 9.3.3)

VTE	Outcome: VTE risk factor	Defined as $\geq 1$ ICD-10 diagnosis code for VTE while receiving tofacitinib therapy.
Surgery, major	Outcome: VTE risk factor	Defined as $\geq 1$ procedure code for a major surgery while receiving tofacitinib therapy.
MI	Outcome: VTE risk factor	Defined as $\geq$ 1 ICD-10 diagnosis code for an MI while receiving tofacitinib therapy.
Heart failure	Outcome: VTE risk factor	Defined as $\geq$ 1 ICD-10 diagnosis code for heart failure while receiving tofacitinib therapy.
Use of combined hormonal contraceptives or hormonal replacement therapy	Outcome: VTE risk factor	Defined as ≥1 prescription dispensing of a combined hormonal contraceptives and/or hormonal replacement therapy (as identified by ATC codes) while receiving tofacitinib therapy.
Inherited coagulation disorder	Outcome: VTE risk factor	Defined as ≥1 ICD-10 diagnosis code for inherited coagulation disorder while receiving tofacitinib therapy.
Malignancy (non- metastatic and metastatic; excluding non-melanoma skin cancer)	Outcome: VTE risk factor	Defined as ≥1 ICD-10 diagnosis code for malignancy (excluding non-melanoma skin cancer) while receiving tofacitinib therapy.
Diabetes	Outcome: VTE risk factor	Defined as ≥1 ICD-10 diagnosis code for diabetes while receiving tofacitinib therapy.

Variable	Role	Operational definition
Hypertension	Outcome: VTE risk factor	Defined as ≥1 ICD-10 diagnosis code for hypertension while receiving tofacitinib therapy.
Discontinuation of tofacitinib after developing ≥1 VTE risk factors while taking tofacitinib	Outcome: VTE risk factor	Defined as ≥1 VTE risk factor while receiving tofacitinib therapy (as listed and defined above) PLUS 0 prescription dispensings for tofacitinib within a specific time window after the code for the VTE risk factor.
		Note: The time window for when to look for a tofacitinib prescription dispensing will be specific to the VTE risk factor acquired while receiving tofacitinib therapy and will be operationalized during SAP development.
		Duration of tofacitinib therapy defined in Section 9.3.3.

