### 9.7.1.2.2.1. Compliance to recommendations for limitations of use

### 9.7.1.2.2.1.1. Patients with VTE risk factors

The proportion of patients with one or more risk factors for VTE, identified prior to tofacitinib initiation, will be described and tabulated overall and by individual VTE risk factor (e.g., prior VTE, recent MI). Proportions will be stratified by "RA or PsA" and "UC."

The total number of VTE risk factors identified prior to tofacitinib initiation will also be described continuously and stratified by "RA or PsA" and "UC."

The proportion of patients diagnosed with UC, one or more VTE risk factors identified prior to tofacitinib initiation, and no use of an alternative therapy (i.e., biologic) prior to tofacitinib

<sup>oo The study outcomes that contain an ADD component will *not* be assessed in Hungary or the Netherlands. The Hungarian administrative claims database is unable to estimate ADD, either directly or by proxy, due to how tofacitinib is captured in the database. In the high-budget impact medication dataset of the PHARMO Database Network (Netherlands), neither ADD nor the number of pills per prescription is captured.

<sup>pp In GKV claims, outpatient diagnoses are reported quarterly.

<sup>qq Hungary will not have a VTE Reporting Period 1. Hungary will also not have a VTE Reporting Period 2 for PsA and UC.

<sup>IT This outcome (and all sub-outcomes) will not be assessed in Sweden because the Swedish national health registers do not capture the laboratory tests of interest. In GKV claims, it may not be possible to differentiate an ALC laboratory test from an ANC laboratory test, or an ALT laboratory test from an AST laboratory test. In the PHARMO Database Network, TB screening and viral hepatitis B and C testing are not captured.

initiation whose ADD in Week 16 through Week 23, Week 24 through Week 31, Week 32 through Week 39, and Week 40 through Week 47 was >10 mg will be described and tabulated.

The proportion of patients who discontinue tofacitinib after developing one or more VTE risk factors while taking tofacitinib will be described and tabulated overall and by individual VTE risk factor (e.g., VTE, MI). Proportions will be stratified by "RA or PsA" and "UC."

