#### 9.7.1.3.1. Use in patients with VTE risk factors

The proportion of patients with one or more risk factors for VTE, identified prior to tofacitinib initiation, will be described and tabulated overall and for each individual VTE risk factor (e.g., prior VTE, recent MI) for VTE Reporting Period 1, VTE Reporting Period 2, and VTE Reporting Period 3.vv Proportions will be stratified by "RA or PsA" and "UC."

The total number of VTE risk factors identified prior to tofacitinib initiation will also be described continuously for VTE Reporting Period 1, VTE Reporting Period 2, and VTE Reporting Period 3vv and stratified by "RA or PsA" and "UC."

The proportion of patients diagnosed with UC, one or more VTE risk factors identified prior to tofacitinib initiation, and no use of an alternative therapy (i.e., biologic) prior to tofacitinib initiation whose ADD in Week 16 through Week 23, Week 24 through Week 31, Week 32 through Week 39, and Week 40 through Week 47 was >10 mg will be described and tabulated for VTE Reporting Period 1, VTE Reporting Period 2, and VTE Reporting Period 3.vv

The proportion of patients who discontinue tofacitinib after developing one or more VTE risk factors while taking tofacitinib will be described and tabulated overall and for each individual VTE risk factor (e.g., VTE, MI) for VTE Reporting Period 1, VTE Reporting

ss Patients with  $\geq 2$  dispensings of tofacitinib are more likely to have taken tofacitinib for the full days' supply of the prescription as opposed to patients with only 1 dispensing of tofacitinib.

<sup>tt The study outcomes that contain an ADD component will *not* be assessed in Hungary or the Netherlands. The Hungarian administrative claims database is unable to estimate ADD, either directly or by proxy, due to how tofacitinib is captured in the database. In the high-budget impact medication dataset of the PHARMO Database Network (Netherlands), neither ADD nor the number of pills per prescription is captured.

<sup>uu In GKV claims, outpatient diagnoses are reported quarterly.

<sup>vv Hungary will not have a VTE Reporting Period 1. Hungary will also not have a VTE Reporting Period 2 for PsA and UC.

<sup>ww Hungary will not have a CV and Malignancy Reporting Period 1 or a CV and Malignancy Reporting Period 2 for PsA and UC.

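### The UC high-dose maintenance outcome fixes VTE risk-factor status before initiation, so it misses high-dose use after a factor first coded on treatment

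*Protocol*

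**What the plan says.** Section 7 gives the 2019 recommendation: "tofacitinib 10 mg BID for maintenance treatment is not recommended in patients with UC who have known VTE risk factors", with an exception where no suitable alternative is available. The text after Table 2 makes this a named aim, "with additional focus on the use of tofacitinib 10 mg BID as a maintenance treatment for patients with UC".

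The matching outcome sets its risk-factor window in several places, always before initiation:

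- Section 9.7.1.2.2.1.1 requires "one or more VTE risk factors identified prior to tofacitinib initiation, and no use of an alternative therapy".
- Section 9.7.1.3.1 repeats it by VTE Reporting Period: "The proportion of patients diagnosed with UC, one or more VTE risk factors identified prior" to initiation.
- Section 9.3.1 does the same in both the primary and the secondary outcome lists.
- The Table 3 row reads "≥1 VTE risk factor (as listed and defined above); 0 prescription medication dispensings for a biologic". The list above that row is the pre-initiation one: 12 months up to and including the index date, or 3 months for MI.

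The dose condition is an ADD above 10 mg in Weeks 16-23, 24-31, 32-39 and 40-47.

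Table 3 also has a block headed "Assessment of VTE risk factors while receiving tofacitinib therapy". It covers VTE, major surgery, MI, heart failure, hormonal therapy, inherited coagulation disorder, malignancy, diabetes and hypertension. These variables feed only the outcomes on discontinuing or continuing tofacitinib, which carry no dose. The VTE stratification of ADD (Sections 9.3.1, 9.3.4 and 9.7.1.2.1) uses factors present before initiation.

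**The concern.** A maintenance dose is chosen after initiation, and Section 7 speaks of known risk factors. The natural reading is the factors known when that dose is given. The outcome pairs a dose measured from Week 16 onward with a risk status closed at the index date. Patients whose status changes in between are treated as unrestricted, although they belong to the group the recommendation addresses.

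At stake is how well the study describes adherence to this dose restriction, overall and across VTE Reporting Periods. The window is written into the outcome, the Table 3 definition and both analysis sections, so it is a choice the protocol makes and not a detail left to the SAP.

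**Working it through.** **1. The plan's own figure.** Section 9.5: 0.50 × 0.50 × 1.96² / 0.10² = 96.04, hence 97, rounded up to 100 per indication and country. This reproduces. It does not bear on the definition, but it gives a yardstick: a planned half-width of 10 percentage points.

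**2. Timing.** Section 9.3.4 starts the four intervals on Days 113, 169, 225 and 281, with the index date as Day 1. The gaps from index are 112, 168, 224 and 280 days, which is 16, 24, 32 and 40 weeks. Risk status is not updated over any of them.

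**3. A test case.** Take a UC patient aged 50 or under with no coded factor before index, no prior biologic, major surgery coded at Week 10 and an ADD of 20 mg in Weeks 16-47.

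- UC high-dose outcome: not counted, because no factor precedes initiation.
- Continue/discontinue outcomes: appears in the UC stratum under surgery, without dose.
- ADD strata: appears at 20 mg, but among patients without a VTE risk factor.
- UC outcome with ADD of at least 15 mg and no prior biologic, as worded in Section 9.3.1: counted, but without any VTE risk status.

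No table shows high dose after an acquired factor. The same happens to a long-standing condition first coded on treatment. Section 9.9 concedes that 12 months may be too short to capture chronic conditions.

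**4. Direction.** The outcome is a proportion of UC patients. Adding on-treatment factors to the baseline ones leaves the denominator unchanged and can only add to the numerator. Against that count, the planned figure can only be equal or lower.

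**5. Size (assumptions only).** Let p be the share of UC patients with a factor before initiation, and q the share of the rest who gain a coded factor before the dose interval. The documents give neither.

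- Newly at risk per 100 UC patients = 100 × (1 − p) × q
- Share of at-risk patients missed = (1 − p)q / [p + (1 − p)q]

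| p | q | newly at risk per 100 | share of at-risk missed |
|---|---|---|---|
| 30% | 2% | 1.4 | 4.5% |
| 30% | 5% | 3.5 | 10.4% |
| 30% | 10% | 7.0 | 18.9% |
| 50% | 2% | 1.0 | 2.0% |
| 50% | 5% | 2.5 | 4.8% |
| 50% | 10% | 5.0 | 9.1% |
| 70% | 2% | 0.6 | 0.8% |
| 70% | 5% | 1.5 | 2.1% |
| 70% | 10% | 3.0 | 4.1% |

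**6. From at-risk status to the outcome.** The outcome also needs no biologic and an ADD above 10 mg. If half of the newly at-risk patients had no biologic and half of those had that dose (again assumed), the multiplier is 0.5 × 0.5 = 0.25. The outcome would then rise by 0.6 × 0.25 = 0.15 to 7.0 × 0.25 = 1.75 percentage points.

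**The case against.** The strongest defence is that fixing risk status at baseline is a conventional descriptive choice and that acquired factors have outcomes of their own. Several stronger readings that a reader might infer do fail:

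- *That a VTE on treatment goes unmeasured.* Section 7 has a separate recommendation for suspected VTE, which is discontinuation. A UC patient who continues after a VTE code should appear in the continue outcome, reported by individual factor and in the UC stratum, subject to the time window left to the SAP. Only the dose is missing.
- *That this is the only measure of the UC dose restriction.* The ADD ≥15 mg outcome in Section 9.3.1 covers UC patients without a prior biologic whatever their risk status. (Its Table 3 row instead requires at least one biologic, a separate inconsistency.)
- *That the passage on raising the dose after loss of response proves the point.* Its remark, "for these patients, the presence of known risk factors for VTE should be considered", concerns patients who failed alternatives such as TNF inhibitors. Those with a captured biologic in the prior 12 months are excluded whatever the risk-factor window.
- *That every such decision falls at Week 16 or later.* A footnote to Section 9.3.4 allows maintenance from Week 8 or 16. Week 16 is the outcome's own window.
- *That the under-count is known to be large.* The percentages missed are shares of at-risk patients under assumed inputs, not changes in the outcome.

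There are practical limits too. ADD outcomes run only in Sweden and Germany. German outpatient diagnoses carry only a calendar quarter (Section 9.4.4), which is longer than a 56-day interval. The Swedish patient register has no GP encounters (Section 9.4.1). Section 9.9 warns of operational difficulty with acquired VTE factors, but does not say that the UC dose outcome omits these patients.

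These points narrow the finding. None supplies the missing combination of dose and updated risk status.

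**Conclusion.** The concern holds in a limited form. For UC patients without a prior biologic, the outcome leaves out use above 10 mg ADD when the first VTE risk factor is coded on treatment before the dose interval. The recommendation it evaluates does not restrict known factors to those present at index. That reading of known is an inference, though a reasonable one for a maintenance decision.

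The direction is certain relative to a count that adds on-treatment factors; the size is not. Under the assumptions shown, the share of at-risk patients missed runs from 0.8% to 18.9%. The effect on the outcome itself would be well below the planned 10-point half-width. It may be small, because age over 50, diabetes and hypertension already count at baseline. The point affects Sweden and Germany only and leaves the sample size unchanged. The change is worth making because it is cheap and fills a gap in a named focus of the study.

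**What to change.** In Table 3 (the primary-objective row and the secondary-objective row that refers back to it) and in Sections 9.3.1, 9.7.1.2.2.1.1 and 9.7.1.3.1, add a second version of the outcome for Sweden and Germany. For each 8-week interval, count the factor as present if it was identified at baseline or coded while receiving tofacitinib before the interval starts. Report it beside the baseline-only version.

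For German outpatient diagnoses, count only those from a calendar quarter that ended before the interval starts, and state this as a limitation. Sweden's difficulty in separating new from prior VTE does not block the change, since a patient with a coded prior VTE already counts as at risk.

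The cost is one extra row per interval, built from variables already in Table 3. The downsides are approximate dating in Germany and that some tablets dispensed before the new code will be counted. The change concerns measurement only and implies no view on dose or clinical management.

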# Table 2.Dates for full reimbursement of tofacitinib and full distribution of the
original, 2019 Article 20 referral, and 2021 signal evaluation procedure
aRMM materials

Country	Indication	Date of full reimbursement	Date of full distribution of the original aRMM materials	Actual or anticipated date of distribution of 2019 Article 20 refers 2021 signal evaluation procedure aRMM materials	
				2019 Article 20 referral	2021 signal evaluation procedure
Sweden	RA	April 2017	May 2017	March 2020	Q4 2021
	PsA	October 2018	July 2018		
	UC	October 2018	September 2018	-	
Hungary	RA	May 2019	December 2018	September	Q4 2021
	PsA	Anticipated Q1 2023 a	N/A	2020	
	UC	Anticipated Q1 2023 a	N/A	-	
The	RA	May 2017	May 2017	May 2020	Q1 2022
Netherlands	PsA	August 2018	September 2018	-	
	UC	September 2018	September 2018	-	
Germany	RA	May 2017	April 2017	March 2020	Q4 2021
	PsA	June 2018	July 2018		
	UC	July 2018	September 2018		

Abbreviations: aRMM = additional risk minimisation measures; N/A = not applicable; PsA = psoriatic arthritis; Q = quarter; RA = rheumatoid arthritis; UC = ulcerative colitis.

a. Currently available via the Named Patient Program.

A comprehensive plan was proposed to assess the effectiveness of the aRMM program, which consists of the following 2 components:

- 1. Process indicators (i.e., HCPs' receipt and understanding of the aRMM materials); and
- 2. Outcome indicators (i.e., prescribing and clinical practice behaviours with respect to recommendations).

To realise these 2 components, the MAH proposed 2 post-authorisation safety studies with the aim of evaluating the effectiveness of the aRMM program:

1. A survey of tofacitinib prescribers; and
2. A drug utilisation study to assess prescribing patterns of tofacitinib and whether there is evidence that prescribers are compliant with the screening and monitoring recommendations and limitations for use included in the aRMM materials for patients prescribed tofacitinib, as well as any potential off-label use of tofacitinib, contraindicated use, and use with concomitant medications not compatible with tofacitinib.

As a result of the Article 20 benefit-risk reassessment, the MAH will additionally evaluate HCPs' compliance with the new PRAC recommendations and limitations for use to minimise the risk of VTE across all approved indications (i.e., tofacitinib should be used with caution in patients with known VTE risk factors regardless of indication and dosage), with additional focus on the use of tofacitinib 10 mg BID as a maintenance treatment for patients with UC, and use and prior treatments among patients aged 65 years and older treated with tofacitinib. The MAH will also examine tofacitinib prescribing patterns over time, as well as changes in the utilisation of tofacitinib among patients with VTE risk factors and among elderly patients aged  $\geq 65$  years following the updated recommendations and limitations for use. As a result of the 2021 signal evaluation procedure, the MAH will also assess HCPs' compliance with the new EMA recommendations and limitations for use related to tofacitinib use in patients with CV risk factors and use in patients with malignancy risk factors.b The MAH will also examine tofacitinib prescribing patterns over time in the 2021 signal evaluation procedure.

This protocol describes the drug utilisation study (i.e., component 2 described above). Data from this study, together with the findings from the tofacitinib prescriber survey (A3921334), will be used to assess whether the aRMM materials are effective. This non-interventional (NI) study is designated as a Post-Authorisation Safety Study (PASS) and is conducted by the MAH as a Category 3 commitment to the EMA.

